## 5.2 Exclusion Criteria

Patients meeting any of the following criteria are not eligible for study participation:

1. Autoimmune disease requiring active treatment within the past twelve months (Note: vitiligo, type 1 diabetes mellitus, residual hypothyroidism due to autoimmune thyroiditis only requiring hormone replacement, and conditions not expected to recur in the absence of an external trigger are permitted)
2. Condition requiring systemic treatment with either corticosteroids (>10 mg daily prednisone equivalent) or other immunosuppressive medications within 14 days prior to study treatment (Note: inhaled and topical steroids, and adrenal replacement steroid doses > 10 mg daily prednisone equivalent, are permitted in the absence of active autoimmune disease.)
3. Has a history of (non-infectious) pneumonitis/interstitial lung disease that required steroids or has current pneumonitis/interstitial lung disease
4. Current treatment on another therapeutic clinical trial
5. Has received prior therapy with an anti-PD-1, anti-PD-L1, or anti-PD-L2 agent or with an agent directed to another stimulatory or co-inhibitory T-cell receptor (e.g. cytotoxic T-lymphocyte-associated protein 4 [CTLA-4], OX 40 [Tumor necrosis factor receptor superfamily, member 4 (TNFRSF4)], CD137 [tumor necrosis factor receptor superfamily member 9 (TNFRSF9)]) (only applies to ovarian cancer patients in Cohorts 1 and 2)
6. For ovarian patients in both cohorts:
  - a. Patients who progressed during or within 3 months of first line of platinum-based therapy
  - b. Patients with histologically non-epithelial tumors or ovarian tumors with low malignant potential (i.e., borderline tumors) or mucinous tumors
  - c. Patients with evidence of bowel obstruction requiring hospitalization and decompression within the past 30 days
7. Major surgical procedure or significant traumatic injury within 4 weeks prior to study treatment, and must have fully recovered from any such procedure; and no date of surgery (if applicable) or anticipated need for a major surgical procedure planned within the next 6 months (The following situations are not considered to be major procedures and are permitted up to 7 days prior to study treatment: thoracentesis, paracentesis, port placement, laparoscopy, thoracoscopy, tube thoracostomy, bronchoscopy, endoscopic ultrasonographic procedures, mediastinoscopy, incisional biopsies, and routine dental procedures. Core biopsy and skin biopsy do not require a waiting period prior to dosing.)
8. Chest radiotherapy  $\leq$  28 days, wide field radiotherapy  $\leq$  28 days (defined as > 50% of volume of pelvic bones or equivalent), or limited field radiation for palliation  $\leq$  14 days prior to study treatment
9. Pleural effusion or ascites that requires paracentesis in the last 30 days

10. Brain involvement with cancer, spinal cord compression, carcinomatous meningitis, or new evidence of brain or leptomeningeal disease; unless the lesion(s) have been radiated or resected, are considered fully treated and inactive, are asymptomatic, and no steroids have been administered for CNS disease over the 7 days prior to study treatment
11. Angina, myocardial infarction (MI), symptomatic congestive heart failure, cerebrovascular accident, transient ischemic attack (TIA), arterial embolism, pulmonary embolism, percutaneous transluminal coronary angioplasty (PTCA), or coronary artery bypass grafting (CABG) within 6 months prior to study treatment
12. Thrombolytic use (except to maintain IV catheters) within 10 days prior study treatment
13. Known active or chronic Hepatitis B or Hepatitis C, other hepatitides (non-alcohol steatohepatitis, alcohol or drug-related, autoimmune) serology at screening or cirrhosis
14. Any active infection requiring parenteral treatment
15. History of hemorrhage or hemoptysis (> ½ teaspoon bright red blood) within 3 months prior to study treatment
16. Known human immunodeficiency virus (HIV) unless CD4+ T cell count > 350 cells/ $\mu$ L with an undetectable viral load
17. Pregnancy or breastfeeding - Female patients must be surgically sterile (i.e.,  $\geq$  6 weeks following surgical bilateral oophorectomy with or without hysterectomy or tubal ligation) or be postmenopausal for at least one year or must agree to use effective contraception during the study and for 5 months following last dose of TJ004309. All female patients of reproductive potential must have a negative pregnancy test (serum or urine) within 72 hours prior to study treatment. Male patients must be surgically sterile or must agree to use effective contraception during the study and for 5 months following last dose of TJ004309
18. Patients with any severe infection within 4 weeks prior to initiation of study treatment, including, but not limited to, hospitalization for complications of infections should not be enrolled in the trial. Patients who required IV antibiotics or were treated with antiviral medications within this 4 week period should be discussed with the Sponsor Medical Monitor prior to enrollment
19. Other severe acute or chronic medical or psychiatric condition or laboratory abnormality that may increase the risk associated with study participation or may interfere with the interpretation of study results and, in the judgment of the Investigator, would make the patient inappropriate for this study

### 5.3 Lifestyle Considerations

There are no lifestyle restrictions in this study.

## 5.4 Meals and Dietary Restrictions

Participants should maintain a normal diet unless modifications are required to manage an AE such as diarrhea, nausea, or vomiting.

## 5.5 Screen Failures

Screen failures are defined as patients who consent to participate in the clinical study but are not subsequently enrolled. A minimal set of screen failure information is required to ensure transparent reporting of screen failure participants to meet the Consolidated Standards of Reporting Trials (CONSORT) publishing requirements and to respond to queries from regulatory authorities. Minimal information includes demography, screen failure details, eligibility criteria, and any SAE.

One additional rescreening may be performed for individuals who initially do not meet the criteria for participation in this study (screen failure). Rescreened patients should be assigned the same participant number as for the initial screening.

## 6 STUDY TREATMENT

The study drug(s) being administered in this study are TJ004309 and atezolizumab.

### 6.1 Description, Storage, Packaging and Labeling

TJ004309 is a recombinant humanized IgG1 antibody that binds to and inhibits the biologic activity of CD73. TJ004309 is produced in CHO cells. TJ004309 will be supplied by the Sponsor as 150 mg/3 mL (50 mg/mL) solution in a sterile single-use vial.

The study drug will be stored according to the instructions on the label or according to instructions provided in a separate document. TJ004309 vials are stored under refrigeration at 2°C to 8°C (36°F to 46°F) and protected from light. Study drug will be stored at the study site in a location that is locked with restricted access. The Investigator or designee must confirm appropriate temperature conditions have been maintained during transit for all study drug received and any discrepancies are reported and resolved before use of the study drug.

Only patients enrolled in the study may receive study drug and only authorized study site personnel may supply or administer study drug. All study drugs must be stored in a secure, environmentally controlled and monitored (manual or automated) area in accordance with the labeled storage conditions with access limited to the Investigator and authorized site staff.

Further guidance and information for the final disposition of unused study drugs are provided in the Pharmacy Manual.

The treatment to be used in this study is outlined in [Table 5](#).

**Table 5: Study Drug Treatments**

Study Treatment	Formulation	Unit Dose Strengths	Dose Levels	Route of Administration	Regimen/Treatment Period	Sourcing
TJ004039	Solution for infusion	150 mg vial	20 mg/kg	IV infusion	Q3W until clinically significant disease progression, unacceptable toxicity, or subject/Investigator decision to withdraw	Provided by the Sponsor
Atezolizumab (Tecentriq®)	Solution for infusion	1200 mg vial	1200 mg flat dose			

### 6.2 Dose Preparation

The preparation, handling, and safe disposal of the study drug should only be prepared by qualified and experienced personnel. TJ004309 will be diluted using aseptic technique. The required dose of TJ004309 will be diluted with 0.9% sodium chloride (normal saline) and administered via an IV infusion pump. TJ004309 dose preparations will be administered with a low protein binding 0.2µm in-line filter. TJ004309 should not be administered as an IV push or bolus. Any unused portion in the vial should be discarded.

The physicochemical in-use stability has been demonstrated for 4 hours at ambient room temperature. Detailed instructions on the preparation and dispensing of TJ004309 are provided in the Pharmacy Manual.

Note that the use of closed system transfer devices (CSTD) for preparation or administration of TJ004309 is not permitted.

For preparation of atezolizumab, see the most recent version of the atezolizumab package insert.

### 6.3 Drug Accountability

The Investigator must maintain an accurate accounting of TJ004309 and atezolizumab supplies. During the study, the following information must be recorded:

- Date of receipt, quantity, and lot number of the study drug received
- Identification number of the patient to whom the product is dispensed
- The date(s) and quantity of the product dispensed
- Dates and quantity of product returned, lost, or accidentally or deliberately destroyed

Investigational Drug Accountability Logs should be maintained by the site and must be readily available for inspection.

### 6.4 Treatment Administration

Intravenous hydration prior to and during therapy is left to the discretion of the Investigator but should be considered for patients that may be volume depleted.

The following premedication will be administered on Cycle 1 Day 1, to be administered within 30 minutes to 2 hours prior to the start of the initial TJ004309 infusion:

- Antipyretic (i.e., acetaminophen 650 mg PO)
- Antihistamine (i.e., diphenhydramine 25 to 50 mg PO/IV, cetirizine 10 mg, etc.)

Premedication is not required for subsequent infusions unless a given patient experiences Grade > 2 infusion related reaction with the immediate prior dose of TJ004309.

TJ004309 will be administered by IV utilizing an infusion pump. TJ004309 is required to be administered with a 0.2 micron downstream filter. The attachment of the infusion pump administration set to the IV bag and transport of the TJ004309 study drug to the patient will be performed as per standard study site procedures. Priming may be done using normal saline. Initially, TJ004309 will be administered over 1 hour ( $\pm$ 15 minutes) in Cycles 1 and 2. In the absence of IRRs in patients infused over 1 hour in Cycle 2, the infusion time of TJ004309 may be reduced to 30 minutes ( $\pm$  10 min) per Investigator's discretion.

When the IV bag containing TJ004309 is empty, flush the IV line with sufficient normal saline to clear the tubing at the same infusion rate as the study drug infusion. The infusion is considered complete when the bag containing TJ004309 is empty including the flush. The dose level, time

of transfer to IV bag, and the infusion start and stop times must be recorded in the source documents. TJ004309 has been demonstrated to be compatible with polyethylene lined, non-DEHP infusion sets and polyvinyl chloride, non-DEHP infusion sets.

Administer atezolizumab 1200 mg IV over 60 minutes on Cycle 1 Day 1. If the patient does not experience any infusion related reactions, the infusion may be administered over 30 minutes starting with Cycle 2. Atezolizumab will be administered on Day 1 of each 21-day cycle until progression according to the package insert, with any dose modifications done per the package insert beginning with Cycle 2 Day 1. Atezolizumab should be administered at least 15 minutes following the completion of TJ004309 administration.

Please refer to the Pharmacy Manual for detailed information.

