### 2.6.2 Potential Risk

TJ004309 is an investigational product, and its safety profile has not been fully established. The occurrence of adverse events associated with TJ004309 treatment from the US dose escalation portion of the study (NCT04322006) includes infusion related reactions, fatigue, pruritis, and diarrhea.

All therapeutic mAb used for cancer treatment have the potential to cause infusion reactions. Symptoms vary with a wide spectrum of severity, ranging from mild fever and chills to life-threatening anaphylaxis with bronchospasm, and hypotension. Typically, infusion reactions to mAb develop within 30 to 120 minutes after the initiation of drug infusion, although symptoms may not show up until 24 hours. The majority of reactions occur after the first or second exposure to drug, although it can also occur during subsequent treatments. The risk of an infusion reaction declines with each subsequent course of therapy.

The most common symptoms of infusion-related reactions are fever/chills, nausea, vomiting, diarrhea, itching/flushing, rash, changes in blood pressure and pulse rate, dyspnea, chest discomfort, back and abdominal pain. Although the exact mechanism of infusion-related

reactions caused by mAb is not fully clear, most likely it is a result of antibody-antigen interactions resulting in cytokine release.

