## 4 STUDY DESIGN

### 4.1 Overall Design

This is a multicenter, open label, Phase 2 study of TJ004309 in combination with atezolizumab in patients with advanced or metastatic solid tumors. This clinical study will be conducted in two parts. Part 1 of the study will include two cohorts: Cohort 1 will include Immuno-Oncology (IO) treatment naïve ovarian cancer patients who have progressed on or after platinum therapy; and Cohort 2 will include patients with head and neck squamous cell carcinoma (HNSCC), non-small cell lung cancer (NSCLC), gastric cancer (GC), triple negative breast cancer (TNBC), or ovarian carcinoma with PD-L1 expression  $\geq 1\%$  (Table 1). All subjects will be evaluated for antitumor activity on a regular basis as specified in the protocol and their clinical status classified according to RECIST 1.1 and iRECIST. Treatments may continue until clinically significant disease progression, unacceptable toxicity, or subject/Investigator decision to withdraw. Based on the efficacy observation in Part 1, Part 2 of the study will further evaluate the efficacy in selected targeted patient populations and will be initiated after reaching agreement with the regulatory agency.

TJ004309 will be given in combination with atezolizumab 1200 mg every 3 weeks (Q3W) beginning with Cycle 1 Day 1 (C1D1). Premedication will be given prior to the initial infusion of TJ004309 to mitigate infusion related reactions. Each cycle will be 21 days in duration.

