**Table 7: TJ004309 Treatment Management Guidelines for Adverse Events (Non-Hematological Toxicities)**

Adverse Event	Grade	Management Actions*
Infusion Related Reactions (IRR) 	Grade 2	
 
Interrupt or slow the rate of infusion. Monitor and if the reaction worsens, stop infusion.
 
Administer institutional standard medications for hypersensitivity reaction as medically indicated. Monitor symptoms until stable. Re-initiate infusion if patient is stable at a 50% slower rate. Prophylactic medications indicated for <math>\leq</math> 24 hours.
 
For subsequent infusions, administer premedication with the following or per institutional standard:           
 
H-1 antihistamine: Diphenhydramine 25-50 mg PO or IV 30 minutes prior to infusion
 
Acetaminophen 500-1000 mg PO 30 minutes prior to infusion
 
Corticosteroids such as dexamethasone (or equivalent) or anti- emetics such as ondansetron (or equivalent) may be administered based on clinical presentation of previous IRR
 
 
 
For subsequent infusions, may administer TJ004309 at a 50% slower rate.
 

	Grade $\geq$ 3	
 
Stop infusion immediately and discontinue TJ004309.
 
Administer epinephrine, bronchodilators, antihistamines, glucocorticoids, IV fluids, vasopressors, oxygen, etc. as medically indicated. Contact sponsor to report SAE.
 
Increase monitoring of vital signs as medically indicated until stable.
 

Chills	Grade 3	
 
Stop the infusion.
 
Administer aggressive symptomatic therapy per institutional standard.
 
After resolution of all symptoms, treatment can be resumed at slower rate, unless severe reaction. If severe reaction, then withhold TJ004309 per Investigator's discretion of clinical presentation of the subject.
 

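### Sections 6.4 and 6.8.3 ask for later premedication only after a Grade > 2 infusion related reaction, but Table 7 orders it after Grade 2 and discontinues TJ004309 at Grade ≥ 3

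*Protocol*

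**What the plan says.** Section 4.1 gives the purpose of premedication: "Premedication will be given prior to the initial infusion of TJ004309 to mitigate infusion related reactions". Sections 6.4 and 6.8.3 specify an antipyretic and an antihistamine before the first TJ004309 infusion on Cycle 1 Day 1. For later infusions both sections use the same sentence: "Premedication is not required for subsequent infusions unless a given patient experiences Grade > 2 infusion related reaction with the immediate prior dose".

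Table 7 in Section 6.9 covers management of IRRs. Its Grade 2 row says: "For subsequent infusions, administer premedication with the following or per institutional standard". It lists an H-1 antihistamine and acetaminophen. Corticosteroids or anti-emetics are optional: they "may be administered based on clinical presentation of previous IRR". The same row allows later infusions at half the rate. The Grade ≥ 3 row says: "Stop infusion immediately and discontinue TJ004309".

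Neither 6.4 nor 6.8.3 refers the reader to Table 7 on premedication. A footnote to Table 7 leaves its actions to the physician's discretion, and Section 6.9 appeals to medical judgment in general.

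**The concern.** The same safety instruction appears in two forms with different grade thresholds. The sections that a site would naturally open when preparing an infusion set the trigger at Grade 3 or higher. The table it would open when managing a reaction sets it at Grade 2 and ends TJ004309 dosing above that.

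The two forms diverge at the infusion after a Grade 2 reaction. That timing matters, because Section 2.6.2 says of antibody infusion reactions in general: "The majority of reactions occur after the first or second exposure to drug". A patient who reacted at Grade 2 in Cycle 1 could receive the second infusion without the protection that Table 7 intends, and the site could point to Section 6.4 in support. What is at stake is patient safety and consistent conduct across sites, not a statistical quantity.

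**Working it through.** **Step 1: the texts by grade of the IRR at the immediately preceding dose.**

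| IRR grade | Sections 6.4 and 6.8.3: later premedication | Table 7 |
|---|---|---|
| 1 | Not required | No IRR row for this grade |
| 2 | Not required | Premedicate later infusions |
| ≥ 3 | Required | Stop and discontinue TJ004309 |

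Grade > 2 on the CTCAE scale is Grade 3 or higher. At those grades Table 7 leaves no later TJ004309 infusion to premedicate. At Grade 2 there is a later infusion, and the texts differ. So in the only row where Table 7 orders premedication, the two sections say it is not required. In the only row where the two sections require it, Table 7 ends dosing.

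**Step 2: how often each row arose in Phase 1.** Inputs are from Protocol Table 4 (Study 4309ST101, N = 20): 2 Grade 1, 11 Grade 2 and 0 Grade 3 to 5.

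- Total: 2 + 11 + 0 = 13, and 13/20 = 65.0%. This matches the figure in Table 4 and Section 4.3.
- Patients for whom 6.4 would have required later premedication: 0 of 13.
- Patients for whom Table 7 would have ordered it: 11 of 13 (84.6%), or 11/20 = 55.0% of those treated.
- Exact (Clopper-Pearson) 95% interval for 11/20: lower limit = Beta quantile(0.025; 11, 10) = 31.5%; upper limit = Beta quantile(0.975; 12, 9) = 76.9%.
- Exact upper limit for 0/20: 1 − 0.025^(1/20) = 16.8%.

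**Step 3: a ceiling for this trial.** Assume that the Phase 1 Grade 2 rate carries over.

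- Both cohorts full (30 + 30 = 60): 60 × 0.55 = 33, or about 19 to 46 over the interval.
- Cohort 1 stopped at 15 (15 + 30 = 45): 45 × 0.55 = 24.75, about 25; 45 × 0.315 = 14.2 and 45 × 0.769 = 34.6, so about 14 to 35.
- If premedication before the first dose lowers the rate to an assumed 20% or 10%: 60 × 0.20 = 12, or 60 × 0.10 = 6.

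These are patients to whom the conflicting texts would apply. The number dosed without premedication is that count × (share who receive another infusion) × (share whose site follows 6.4 or 6.8.3 rather than Table 7). The documents give neither share. If every site follows Table 7, the product is 0.

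**The case against.** The strongest reply is that there is no conflicting command. Wording that premedication is not required does not forbid it, so a site that follows Table 7 complies with both texts. A site managing a Grade 2 reaction also needs Table 7 to decide whether to interrupt, slow or restart the infusion, and the premedication order is in the same cell. This stands as far as it goes, and it is why the number of patients affected may be close to zero. It does not make the threshold in the two sections right.

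The discretion wording is a weaker reply. It applies to all of Table 7's actions and does not say which threshold was intended. It does limit one inference. A reader might conclude that the Grade > 2 trigger can never apply to anyone. The documents do not support that absolute form, because a physician using the footnote's discretion might dose again after Grade 3. The claim holds only on the condition that Table 7 is followed.

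A reader might also see a second contradiction in Table 7's Grade 3 chills row, which says: "After resolution of all symptoms, treatment can be resumed at slower rate, unless severe reaction". No precedence is stated for chills that are part of a Grade ≥ 3 IRR. But the row can be read as covering isolated chills, and it already excludes resumption after a severe reaction. It is an unstated rule with a workable reading, not an error.

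Finally, the symbol may be a slip for ≥, or a mark lost in text extraction. The same symbol appears in both sections, while ≥ survives elsewhere, including Section 6.9 and Table 7. The signed copy should be checked. A slip in the signed text would still need correcting.

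**Conclusion.** The sentence in Sections 6.4 and 6.8.3 is wrong as written when set against the protocol's own management table, and nothing else in the documents reconciles the two. It is a minor safety-conduct correction.

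At the Phase 1 rate, up to about 33 of 60 patients (about 25 of 45) would meet the conflicting texts. That rests on 20 patients pooled across doses of 5 to 20 mg/kg and two schedules. The documents do not describe Phase 1 premedication, and premedication before the first dose here may lower the rate.

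A reader might take 33 as the number left unprotected. The documents do not support that: it is a ceiling, and the actual number is unknown. A reader might also expect distorted infusion-modification tables (SAP Section 7) or an effect on response rate or the Cohort 1 futility look. The first is conjecture, and nothing in the documents points to the second.

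Harm is probably modest. Phase 1 reactions were Grade 1 or 2 and resolved at later infusions (Sections 2.5 and 4.3), and Section 2.6.2 says the risk falls with each course. SAP Section 4.1 records that Part 2 was not started, so the correction matters for any remaining dosing and for reuse of the text in later protocols.

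**What to change.** In Sections 6.4 and 6.8.3, replace the sentence with: *Later TJ004309 infusions need no premedication unless the patient has had a Grade 2 IRR to TJ004309, in which case premedicate them as in Table 7; after a Grade ≥ 3 IRR, TJ004309 is discontinued (Table 7).*

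If the sponsor wants premedication to lapse after a reaction-free infusion, state that in Table 7 and in both sections, since 6.4 looks only at the immediately preceding dose and Table 7 sets no such limit.

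The cost is one sentence in two places and a note to sites. The downside is some extra antihistamine and acetaminophen after Grade 2 reactions at sites that had relied on 6.4 or 6.8.3. Corticosteroids stay optional under Table 7, so the change forces no steroid use alongside atezolizumab.
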